APPENDIX A: Schedule of Treatment and Evaluations

	Screening -21 Days	Cycle 1	Cycle 2	Cycle 3	Cycle 4	Cycle 5	Cycle 6	End of Treatment ¹⁴	Every 2 or 3 mo. ¹³	Follow Up ¹²
Signed informed consent	X									
Review inclusion/exclusion	X	X								
Medical history ¹	X									
Physical examination	X	X	X	X	X	X	X	X ¹⁶	X	
Height (cm)	X									
Weight (kg)	X	X	X	X	X	X	X			
BSA calculation ²		X	X	X	X	X	X			
Vital signs ³	X	X	X	X	X	X	X	X		
ECOG PS	X	X	X	X	X	X	X	X		
CT/ MRI scan / tumor measurements ⁴	X ^{8a}			X ⁸			X ⁸	X ¹⁰	X ⁸	
ECG	X	X	X	X	X	X	X	X ¹¹	X	
ECHO (with ejection fraction) or MUGA/cardiac ultrasound	X		X		X		X	X	X	
CBC w/differential & plts ⁵	X	X ¹⁶	X	X	X	X	X	X ¹¹	X	
Serum chemistries ^{5, 6}	X	X ¹⁶	X	X	X	X	X	X ¹¹		
Urinalysis ⁷	X							X ¹¹		
Serum troponin	X	X ¹⁶	X	X	X	X	X	X ¹¹	X	
Serum/urine pregnancy test	X									
Randomization		X ¹⁵								
INNO-206 or doxorubicin admin administration ¹⁷		X	X	X	X	X	X			
Blood alcohol level ¹⁸		X	X	X	X	X	X			
Concomitant medications	X ⁹	X	X	X	X	X	X	X		
Adverse events	X	X	X	X	X	X	X	X		
Telephone call										X

NOTE: All assessments must be performed within 72 hr of each specified time parameter, except Cycle 1 (see Section 7 for details).

CLINICAL PROTOCOL

TITLE: A Multicenter, Randomized, Open-Label Phase 2b Study to Investigate the Preliminary Efficacy and Safety of INNO-206 (Doxorubicin-EMCH) Compared to Doxorubicin in Subjects with Metastatic, Locally Advanced, or Unresectable Soft Tissue Sarcoma

PROTOCOL NUMBER: INNO-206-P2-STS-01

STUDY DRUG: INNO-206

IND NUMBER: 113,695

EUDRACT NUMBER: 2011-004927-11

SPONSOR: CytRx Corporation
[name]
[name]
[contact]
[contact]

SAFETY HOTLINE: Toll-free: [name]

SAFETY FAX: Toll-free: [name]

DATE OF PROTOCOL: November 14, 2011

AMENDMENT 1: December 16, 2011

AMENDMENT 2: April 15, 2012

CONFIDENTIAL

The information contained in this document is confidential and the proprietary property of CytRx Corporation. Any unauthorized use or disclosure of such information without the prior written authorization of CytRx Corporation is prohibited.

PROTOCOL SIGNATURE PAGE

A Multicenter, Randomized, Open-Label Phase 2b Study to Investigate the Preliminary Efficacy and Safety of INNO-206 (Doxorubicin-EMCH) Compared to Doxorubicin in Subjects with Metastatic, Locally Advanced, or Unresectable Soft Tissue Sarcoma

1. SYNOPSIS

Name of Sponsor/Company: CytRx Corporation	
Protocol Number: INNO-206-P2-STS-01	Phase of Development: 2b
Title of the Protocol: A Multicenter, Randomized, Open-Label Phase 2b Study to Investigate the Preliminary Efficacy and Safety of INNO-206 (Doxorubicin-EMCH) Compared to Doxorubicin in Subjects with Metastatic, Locally Advanced, or Unresectable Soft Tissue Sarcoma	
Primary Objectives: The primary objective of this study is to determine the preliminary efficacy of administration of INNO-206 compared to doxorubicin in subjects with metastatic, locally advanced, or unresectable soft tissue sarcoma as measured by progression-free survival, progression-free survival at 4 and 6 months, tumor response and overall survival.	
Secondary Objectives: The secondary objective of this study is to evaluate the safety of INNO-206 compared to doxorubicin in this population assessed by the frequency and severity of adverse events (AEs), abnormal findings on physical examination, laboratory tests, vital signs, multiple-gated acquisition (MUGA) scans/cardiac ultrasound evaluations, electrocardiogram (ECG) results, and weight.	
Study Rationale and Significance: INNO-206 is a novel prodrug that binds covalently to albumin in the circulation. The drug is accumulated in tumors and doxorubicin is released in the tumor by cleaving the acid labile linker (EMCH) in the low pH tumor environment. This carrier-linked prodrug has demonstrated enhanced anti-tumor activity with reduced toxicity in several murine models when compared with free doxorubicin. Patients with metastatic, locally advanced, or unresectable soft tissue sarcomas have a poor prognosis with progression-free survival of around 4-5 months and median overall survival of approximately 15 months. Three-year survival rates as high as 30% have been observed in some clinical studies. Several chemotherapy regimens have been explored as palliative therapy for subjects with advanced soft tissue sarcomas. Combinations of ifosfamide and doxorubicin appear to offer the highest response rates and longest time to progression. However, these regimens are quite toxic and have not significantly increased survival in these individuals. INNO-206 may improve the activity of doxorubicin without increasing its toxicity as has been demonstrated in animal studies.	

Name of Sponsor/Company: CytRx Corporation	
Protocol Number: INNO-206-P2-STS-01	Phase of Development: 2b

Study Design and Methodology: This is a phase 2b open-label study evaluating the preliminary efficacy and safety of INNO-206 administered at 350 mg/m² (260 mg/m² doxorubicin equivalent) intravenously (IV) on Day 1 every 21 days for up to 6 consecutive cycles compared to doxorubicin administered at 75 mg/m² for up to 6 consecutive cycles. Subjects will be randomized 2:1 to receive either INNO-206 or doxorubicin.
 
Subjects will visit the study site every 21 days for their IV infusions, at which time safety monitoring, including AEs, a directed physical examination, laboratory evaluations (serum chemistry, complete blood count [CBC], and urinalysis), vital signs, weight measurements, ECOG performance status and ECGs will be performed. Cardiac function will also be followed periodically using either MUGA scans or cardiac ultrasounds. Treatment will continue every 21 days until tumor progression is observed, 6 cycles of treatment are completed or unacceptable toxicity occurs.
 
Tumor response will be monitored every 6 weeks from Cycle 1-Day 1 during treatment, at End of Treatment, 2 months following the End of Treatment scan (for those subjects completing 6 cycles), and then every 3 months until disease progression using the Response Evaluation Criteria in Solid Tumors (RECIST) 1.1 criteria. For those subjects that leave the study prior to completing Cycle 6, and who do not start another therapy, they can be followed 2 months following the End of Treatment scan, and then every 3 months until disease progression. However, if a subject receives another therapy, they should only be followed for overall survival [OS]. Progression-free survival [PFS], progression-free survival at 4 and 6 months and OS will be monitored as other primary objectives.
	

Name of Sponsor/Company: CytRx Corporation	
Protocol Number: INNO-206-P2-STS-01	Phase of Development: 2b

Study Population and Main Criteria for Inclusion/Exclusion:
 
Inclusion Criteria:
 
Subjects must meet the following criteria to be included in the study:
 
 1. Age between 15-80 years (US only), and 18-80 (rest of world (ROW)), male or female. 2. Adjuvant or neoadjuvant chemotherapy (including doxorubicin) allowed if no tumor recurrence for at least 12 months since the last measurement, beginning or end of last chemotherapy. 3. Histologically or cytologically confirmed, locally advanced, unresectable, and/or metastatic soft tissue sarcoma of intermediate or high grade. 4. Capable of providing informed consent and complying with trial procedures. 5. ECOG performance status 0-2. 6. Life expectancy >12 weeks. 7. Measurable tumor lesions according to RECIST 1.1 criteria. 8. Women must not be able to become pregnant (eg post-menopausal for at least 1 year, surgically sterile, or practicing adequate birth control methods) for the duration of the study. (Adequate contraception includes: oral contraception, implanted contraception, intrauterine device implanted for at least 3 months, or barrier method in conjunction with spermicide.) 9. Women of child bearing potential must have a negative serum or urine pregnancy test at the Screening Visit and be non-lactating. 10. Geographic accessibility to the site that ensures the subject will be able to keep all study-related appointments. 
Exclusion Criteria:
 
Subjects meeting the following criteria will not be enrolled:
 
 1. Prior chemotherapy unless for adjuvant or neoadjuvant therapy with no tumor recurrence for at least 12 months. 2. Prior exposure to >3 cycles or 225 mg/m² of doxorubicin or Doxil[®]. 3. Palliative surgery and/or radiation treatment less than 4 weeks prior to Randomization. 4. Exposure to any investigational agent within 30 days of Randomization. 5. Current Stage 1 or 2 soft tissue sarcomas. 6. Current evidence/diagnosis of alveolar soft part sarcoma, chondrosarcoma, rhabdomyosarcoma, osteosarcoma, gastrointestinal stromal tumor (GIST), dermatofibrosarcoma, Ewing's sarcoma, Kaposi's sarcoma, mixed mesodermal tumor, clear cell sarcomas and unresectable low grade liposarcomas. 7. Central nervous system metastasis 8. History of other malignancies except cured basal cell carcinoma, superficial bladder cancer or carcinoma in situ of the cervix unless documented free of cancer for ≥5 years. 9. Laboratory values: Screening serum creatinine >1.5x upper limit of normal (ULN), alanine aminotransferase (ALT) > 3 × ULN or >5 × ULN if liver metastases are present, total bilirubin >3 × ULN, absolute neutrophil count <1,500/mm³, platelet concentration <100,000/mm³, hematocrit level <25% for females or <27% for males, coagulation tests (prothrombin time [PT], partial thromboplastin time [PTT], International Normalized Ratio [INR]) >1.5 × ULN, and albumin <2.0 g/dL. 10. Clinically evident congestive heart failure > class II of the New York Heart Association (NYHA) guidelines. 	

Name of Sponsor/Company: CytRx Corporation	
Protocol Number: INNO-206-P2-STS-01	Phase of Development: 2b

11. Current, serious, clinically significant cardiac arrhythmias, defined as the existence of an absolute arrhythmia or ventricular arrhythmias classified as Lown III, IV or V.
 
12. Baseline QTc >470 msec and/or previous history of QT prolongation while taking other medications. Concomitant use of medications associated with a high incidence of QT prolongation is not allowed
 
13. History or signs of active coronary artery disease with or without angina pectoris.
 
14. Serious myocardial dysfunction defined as scintigraphically (eg MUGA, myocardial scintigram) or ultrasound determined absolute left ventricular ejection fraction (LVEF) <45% of predicted.
 
15. History of HIV infection.
 
16. Active, clinically significant serious infection requiring treatment with antibiotics, anti-virals or anti-fungals.
 
17. Major surgery within 3 weeks prior to Randomization.
 
18. Substance abuse or any condition that might interfere with the subject's participation in the study or in the evaluation of the study results.
 
19. Any condition that is unstable and could jeopardize the subject's participation in the study.
	

Number of Subjects: One hundred and five (105) study subjects will be randomized 2:1 (INNO-206:doxorubicin) at approximately 30 study centers in the United States (US), Hungary, Romania, Ukraine, Russia, India, and Australia. Up to 32 subjects may be enrolled in India, with the remaining subjects distributed in the other locations.
	

Test Product, Dose and Mode of Administration: Lyophilized powder in vials that contain 200 mg of INNO-206 reconstituted by adding a solution of 50% ethanol: 50% sterile water, administration completed within 2 hours (of being reconstituted) as a 30 minute IV infusion in Lactated Ringer's solution. Total dose of 350 mg/m² (260 mg/m² doxorubicin equivalent).
	

Reference Therapy, Dose and Mode of Administration: Doxorubicin HCl Injection is a sterile parenteral, isotonic available in 5 mL (10 mg), 10 mL (20 mg), 25 mL (50 mg) single dose vials. Each mL contains doxorubicin HCl and the following inactive ingredients: NaCl (0.9%) and water for injection q.s. Hydrochloric acid is used to adjust the pH to a target of pH of 3.0. Prepare IV infusion per the package insert (see the Study Reference Manual).
	

Criteria for Evaluation:
 
Efficacy: The following efficacy variables will be evaluated as noted:
 
 • Progression-free survival • Overall survival • Objective tumor response (RECIST 1.1 criteria) • 4 and 6 month progression-free survival 
Safety: The following safety variables will be assessed over the duration of the study:
 
 • Adverse events • Ability to remain on assigned treatment (tolerability) • Clinical and laboratory data including physical examinations, vital signs, weight, MUGA/cardiac ultrasound evaluations, ECG results and laboratory test results • Use of concomitant medications 	

Name of Sponsor/Company: CytRx Corporation	
Protocol Number: INNO-206-P2-STS-01	Phase of Development: 2b

Statistical Methods: In accordance with the intention-to-treat principle, all randomized subjects who enter active treatment and have had at least 1 dose of study medication and 1 post-dose efficacy measurement will be included in the primary statistical analyses according to the treatment group to which they were originally assigned.
 
Efficacy: Tumor response will be monitored every 6 weeks from Cycle 1-Day1 during treatment, at End of Treatment, 2 months following the End of Treatment scan (for those subjects completing 6 cycles), then every 3 months until disease progression. For the estimation of progression-free and overall survival a Kaplan-Meier analysis will be performed. The percentage of subjects with complete or partial responses, or stable disease will be evaluated at 4 and 6 months.
 
Safety: The safety data will be summarized by treatment group. The treatment groups will be compared with respect to occurrence of each AE. Total number of AEs leading to withdrawal, and abnormal laboratory tests will be compared between groups using Fisher’s exact test. Adverse events, ability to remain on assigned treatment (tolerability), and abnormal findings on physical examinations, vital signs, weight, ECG results, laboratory test results, and use of concomitant medications, will be assessed to characterize the safety profile of the treatment regimens. Descriptive statistics denoting the changes from baseline to the final assessment visit with respect to key laboratory parameters and vital signs will also be provided.
	

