APPENDIX A: Schedule of Treatment and Evaluations

	Screening -21 Days	Cycle 1	Cycle 2	Cycle 3	Cycle 4	Cycle 5	Cycle 6	End of Treatment ¹⁴	Every 2 or 3 mo. ¹³	Follow Up ¹²
Signed informed consent	X									
Review inclusion/exclusion	X	X								
Medical history ¹	X									
Physical examination	X	X	X	X	X	X	X	X ¹⁶	X	
Height (cm)	X									
Weight (kg)	X	X	X	X	X	X	X			
BSA calculation ²		X	X	X	X	X	X			
Vital signs ³	X	X	X	X	X	X	X	X	X	
ECOG PS	X	X	X	X	X	X	X	X		
CT/ MRI scan / tumor measurements ⁴	X ^{8a}			X ⁸		X ⁸		X ¹⁰	X	
ECG	X	X	X	X	X	X	X	X ¹¹	X	
ECHO (with ejection fraction) or MUGA/cardiac ultrasound	X		X		X		X	X	X	
CBC w/differential & plts ⁵	X	X ¹⁶	X	X	X	X	X	X ¹¹	X	
Coagulation tests (PT, PTT, INR)	X									
Serum chemistries ^{5, 6}	X	X ¹⁶	X	X	X	X	X	X ¹¹		
Urinalysis ⁷	X							X ¹¹		
Serum troponin	X	X ¹⁶	X	X	X	X	X	X ¹¹	X	
Serum/urine pregnancy test	X									
Randomization		X ¹⁵								
INNO-206 or doxorubicin admin administration ¹⁷		X	X	X	X	X	X			
Blood alcohol level ¹⁸		X	X	X	X	X	X			
Concomitant medications	X ⁹	X	X	X	X	X	X	X		
Adverse events	X	X	X	X	X	X	X	X		
Telephone call										X

NOTE: All assessments must be performed within 72 hr of each specified time parameter, except Cycle 1 (see Section 7 for details).

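### Later tumor scans are timed from End of Treatment, and Appendix A lists on-treatment scans by cycle, so unequal dose delays can shift PFS with no true drug effect

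*Combined protocol and SAP*

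**What the plan says.** This concerns the Amendment 2 synopsis and its Appendix A, the last set in the file.

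- **Synopsis, Study Design and Methodology (repeated under Statistical Methods).** Scans are due "every 6 weeks from Cycle 1-Day 1 during treatment, at End of Treatment, 2 months following the End of Treatment scan". In full, the post-treatment part reads: "2 months following the End of Treatment scan (for those subjects completing 6 cycles), and then every 3 months until disease progression". Subjects who leave before completing Cycle 6 and start no other therapy are covered by permissive wording: "they can be followed 2 months following the End of Treatment scan". Once another therapy starts, follow-up is for overall survival only.
- **Dosing.** Treatment is given "on Day 1 every 21 days for up to 6 consecutive cycles", and ends at progression, six cycles or unacceptable toxicity.
- **Appendix A.** The row "CT/ MRI scan / tumor measurements" is marked under screening, Cycle 3, Cycle 5, End of Treatment and the 2-or-3-month column. The note below the table reads: "All assessments must be performed within 72 hr of each specified time parameter, except Cycle 1". The footnote texts are not in the supplied file.
- **Endpoints and analysis.** PFS and PFS at 4 and 6 months are among the primary measures. The only PFS method stated is Kaplan-Meier. The supplied text gives no interval-censored or scheduled-date analysis.

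**The concern.** Progression seen on imaging is dated at the scan that shows it. If scan dates depend on dosing, and dosing runs late more often in one arm, the arms are observed at different times. The trial is open-label and compares regimens whose toxicity is expected to differ, so unequal delays are plausible.

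Two features create the dependence. The first is unambiguous: after treatment, every scan is counted from the End of Treatment scan. The second is an unresolved difference between the 6-week text and the Appendix A cycle columns.

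At stake is a false difference in primary measures, and possibly a contradiction between them. A later first post-treatment scan delays the recorded progressions. A later End of Treatment scan that still falls before month 6 picks up more progressions by that landmark.

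**Working it through.** **Inputs from the documents.** Cycles of 21 days, up to six; median PFS around 4-5 months; 105 subjects randomized 2:1, that is 70 and 35; the scan rules above; a 72-hour window.

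**Assumptions not in the documents.** Exponential PFS with median 4.5 months (137 days) in both arms; no deaths before progression; End of Treatment 21 days after the last dose; the delay sizes and frequencies; a two-sided 5% log-rank test. 2 months is taken as 61 days, month 4 as day 122 and month 6 as day 183.

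The supplied text gives no figure for scan-timing error, and no alpha, power or hazard ratio behind the 105, so there is no plan figure to reproduce.

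**Step 1: scan dates.** With a delay of d days per cycle, Cycle k starts on day (21 + d)(k - 1).

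- No delay: Cycle 3 on day 42, Cycle 5 on day 84, last dose on day 105, End of Treatment on day 126, next scan on day 126 + 61 = 187. The text and Appendix A agree.
- d = 7: Cycle 3 on day 56, Cycle 5 on day 112, last dose on day 140, End of Treatment on day 161, next scan on day 222. The 6-week text still puts scans on days 42, 84 and 126.

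**Step 2: landmark rates, every cycle delayed 7 days in one arm (worst case).** The observed rate is S(last scan on or before the landmark), with S(t) = 0.5^(t/137).

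| Arm | Last scan by day 122 | 4-month PFS | Last scan by day 183 | 6-month PFS |
|---|---|---|---|---|
| On time, either reading | 84 | 65.4% | 126 | 52.9% |
| Delayed, Appendix A columns | 112 | 56.7% | 161 | 44.3% |
| Delayed, 6-week text | 84 | 65.4% | 161 | 44.3% |
| True value | - | 54.0% | - | 39.7% |

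The false 6-month gap is 52.9 - 44.3 = 8.6 points under either reading. The 4-month gap is 65.4 - 56.7 = 8.7 points under the Appendix A reading and zero under the 6-week text. With medians of 4 or 5 months the gaps are again 8-9 points. With End of Treatment 30 days after the last dose, the 6-month gap is S(135) - S(170) = 50.5% - 42.3% = 8.2 points.

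**Step 3: partial delays.** Simulation with 15,000 subjects per arm, 7-day delays in 30% vs 5% of cycles, and a ±3-day window gives a hazard ratio of about 0.93-0.95 across the two readings and 6-month PFS of about 50% vs 52%. The more delayed arm looks better on the hazard ratio and worse at 6 months.

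**Step 4: false-positive rate.** With 70 vs 35 subjects, 4,000 runs per scenario and delays of 3-14 days in every cycle of the larger arm, log-rank rejection is 6-9% under the Appendix A reading (hazard ratio 0.89-1.00) and 5-8% under the 6-week text (0.92-1.06). With no imbalance it is 5.0-5.6%.

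**Step 5: early stopping.** If 20-40% stop, spread over Cycles 2-4, the landmark rates move by less than 0.5 point (about 1 point or less with End of Treatment at 30 days). With 10% vs 30-40% stopping, rejection is 5.0-5.7%. Stopping matters only if it clusters: if all stop after Cycle 3, 4-month PFS reads S(63) = 72.7%; if all stop after Cycle 5, S(105) = 58.8%.

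**Step 6: fixed calendar.** With 6-weekly scans from a fixed date, whatever the dosing, both arms read 65.4% at 4 months and S(168) = 42.7% at 6 months under every delay and stopping pattern tested. Log-rank rejection is 5.0-5.5%.

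**The case against.** The strongest reply is that the synopsis states a calendar rule twice. Cycle-driven scanning is inferred from marks in a table whose footnotes, like the Section 7 to which its note refers, are not supplied. The note speaks of a specified time, not of a cycle visit. A clarifying rule may exist. This stands, and it limits the Appendix A half to a request to reconcile. It does not reach the End of Treatment anchor, which the synopsis states outright.

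Three stronger readings are tempting, and the documents do not support them:

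- **That the 4-month rate is distorted in general.** Under the 6-week text, dose delay leaves it unchanged.
- **That unequal early stopping is as harmful as delay.** Spread over several cycles, it has almost no effect.
- **That the rule favors a particular arm, or seriously inflates false positives.** The direction depends on the size of the delay and on the measure, and rejection reaches at most about 9% in deliberately extreme cases. A difference in observed medians should not be quoted either. Observed survival sits near 50% across the gap before the first post-treatment scan, so the delayed arm's median jumped between about 149-163 and 184-186 days in identical repeats.

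The documents give no delay rates, and delay of every cycle in one arm only is a bound. The trial also seeks preliminary efficacy, so modest error matters less than in a confirmatory test.

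**Conclusion.** The concern holds in a limited form. Post-treatment scan dates depend on dosing, and the on-treatment rule is stated in two ways that agree only without delays. With no true effect, a moderate imbalance in delays shifts the hazard ratio to about 0.93-0.95 and 6-month PFS by about 2 points. The worst case is about 9 points at 6 months under either reading, and about 9 points at 4 months only under the Appendix A reading. These sizes rest on exponential PFS with a median near 4.5 months, an assumed End of Treatment date and assumed delay patterns. The distortion is modest, but it affects primary measures, is cheap to prevent and is hard to repair once the scans have been done.

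**What to change.** Reconcile the two synopsis sections and Appendix A:

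1. State one tumor-scan calendar counted from a fixed date (randomization or Cycle 1-Day 1), unaffected by dose delays or stopping and continued after treatment until progression. The existing rule on follow-up after another therapy can stay. One example is weeks 6, 12, 18, about 27, about 40, then every 3 months. Under the 21-day assumption, these are close to the dates an on-time six-cycle completer already has (days 42, 84, 126, 187 and 278).
2. Keep the End of Treatment scan as an extra, not as the anchor, and move the Appendix A scan marks out of the cycle columns.
3. Say how progression first seen on that extra scan is dated. If it counts on its own date, the worst case returns: an extra scan on day 161 falls between days 126 and 189 and again gives 44.3% vs 52.9%. Dating it to the next calendar scan in the PFS comparison removes this. So does adding a calendar scan at week 24 (day 168), because both arms then read 42.7%.
4. Optionally, add an interval-censored or scheduled-date sensitivity analysis of PFS.

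**Cost.** Mainly wording. On-time completers have no added scans unless week 24 is added. Early stoppers may have slightly different or a few more scans, and a scan may fall between dosing visits when a cycle is delayed. Without a week-24 scan, 6-month PFS still reads high (about 53% against a true 40%), but equally in both arms.

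### The primary population is labelled intention-to-treat but requires a dose and an undefined post-dose efficacy measurement, and the synopsis gives no all-randomized set for PFS, OS or response

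*Combined protocol and SAP*

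**What the plan says.** The current text is the synopsis that follows the Amendment 2 title page. Its Statistical Methods entry begins "In accordance with the intention-to-treat principle" and then defines the primary set as "all randomized subjects who enter active treatment and have had at least 1 dose of study medication and 1 post-dose efficacy measurement". Subjects in that set are analysed in the arm to which they were randomized. The two earlier synopses in the file carry the same rule.

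Under Criteria for Evaluation, the statement "The following efficacy variables will be evaluated as noted" introduces PFS, OS, objective response, and PFS at 4 and 6 months. Study Design and Methodology adds that "progression-free survival at 4 and 6 months and OS will be monitored as other primary objectives", so OS is among the primary objectives. On analysis, the synopsis says "For the estimation of progression-free and overall survival a Kaplan-Meier analysis will be performed", and that the percentage with response or stable disease is evaluated at 4 and 6 months. It names no separate population or denominator for any of these.

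On timing, "Tumor response will be monitored every 6 weeks from Cycle 1-Day 1 during treatment", with a further scan at End of Treatment. Subjects who go on to another therapy are followed for OS only.

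**The concern.** Intention-to-treat settles two things: who is included and which arm they count in. The rule keeps the second and gives up the first, because receiving a dose and having a measurement are both events after randomization.

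The term *efficacy measurement* is also not defined in the synopsis, and two readings are open:

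- **Strict reading (a tumor assessment).** Subjects never dosed are excluded, and so are dosed subjects who die or leave before any post-dose scan. The early deaths removed are themselves PFS and OS events. Survival data collected on dosed subjects who changed therapy without a post-dose scan would be discarded.
- **Broad reading (any record on a listed efficacy variable).** PFS and OS are listed as efficacy variables, so a recorded death or survival contact could count. Only never-dosed subjects are then lost.

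Two analysts could build different primary sets from the same sentence, and in an open-label trial the choice might be made after outcomes are visible. On the strict reading the OS and PFS curves are raised and the response denominator shrinks. If exclusions differ by arm, the treatment comparison is biased.

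**Working it through.** **Inputs from the Amendment 2 synopsis.** N = 105, randomized 2:1; first scheduled scan 6 weeks after Cycle 1-Day 1; background median OS about 15 months and PFS about 4 to 5 months (Study Rationale and Significance); life expectancy above 12 weeks (inclusion criterion 6).

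**The plan's own figure.** 105 × 2/3 = 70 and 105 × 1/3 = 35, so the allocation is exact. The synopsis gives no alpha, power, effect size or event count, so 105 itself cannot be reproduced.

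**Step 1: never-dosed subjects (excluded on any reading).** Their number k is not given, so k = 1 to 5 is an assumption. The share removed is k/105. A response rate is multiplied by 105/(105 − k) if none of them would count as a responder.

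| k | Share removed | Response factor |
|---|---|---|
| 1 | 1.0% | 1.010 |
| 3 | 2.9% | 1.029 |
| 5 | 4.8% | 1.050 |

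The effect on OS depends on their prognosis, which is unknown.

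**Step 2: deaths before the first scheduled scan (strict reading only).** Assume a constant hazard. Week 6 is 42/30.4375 = 1.38 months, and P = 1 − 0.5^(1.38/median OS).

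- Median 12 months: P = 0.0766, × 105 = 8.0 subjects
- Median 15 months: P = 0.0618, × 105 = 6.5 subjects (4.3 of 70 and 2.2 of 35)
- Median 18 months: P = 0.0517, × 105 = 5.4 subjects

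**Step 3: effect on the curves.** Let x be the fraction of all subjects dropped as early deaths. Beyond week 6 the retained curve is S(t)/(1 − x). Its median solves S(t)/(1 − x) = 0.5, and PFS at a fixed time becomes PFS(t)/(1 − x). Median OS is 15 months and median PFS 4.5 months, so true PFS is 0.5^(4/4.5) = 54.0% at 4 months and 0.5^(6/4.5) = 39.7% at 6 months.

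| Early deaths dropped | x | Median OS (months) | 4-month PFS | 6-month PFS |
|---|---|---|---|---|
| None | 0 | 15.0 | 54.0% | 39.7% |
| A quarter | 0.0154 | 15.3 | 54.9% | 40.3% |
| Half | 0.0309 | 15.7 | 55.7% | 40.9% |
| All | 0.0618 | 16.4 | 57.6% | 42.3% |

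With all dropped, the rise in 4-month PFS is 3.3, 3.6 and 3.8 points for median PFS of 4, 4.5 and 5 months. The OS shift with all dropped is 1.38 months (6 weeks) whatever the true median. That follows from the constant-hazard assumption and is not evidence of robustness.

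**Step 4: comparison between arms.** Dropping the same fraction in both arms divides both curves by the same (1 − x), so the comparison barely changes. To illustrate unequal exclusion, take identical arms with 6-month PFS p = 39.7%. Drop early failures from the 70-subject arm only, so that p′ = p × 70/(70 − dropped), and form ln p′ / ln p.

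| Dropped of 70 | 6-month PFS | Apparent cumulative-hazard ratio |
|---|---|---|
| 2 | 40.9% | 0.97 |
| 4 | 42.1% | 0.94 |
| 7 | 44.1% | 0.89 |

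These counts, and placing all of them in one arm, are assumptions. Reversing the imbalance would bias the comparison the other way.

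**Step 5: power.** With an assumed HR of 0.50, an 80% event fraction and a two-sided 5% test, power is 85.0% with 105 analysed, 83.1% with 5% excluded and 81.1% with 10% excluded. The issue is mainly bias, not power.

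**The case against.** The strongest case against concerns scope and size rather than the label.

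- **Text not available.** The documents contain only synopses and schedules. Appendix A points to a Section 7, and its footnote markers on scans, End of Treatment, follow-up and randomization have no text here. A definition, a separate OS set or follow-up of undosed subjects may be stated elsewhere. This stands as a limit. A correct section elsewhere would still leave this sentence mislabelling the set.
- **The certain loss is small.** Randomization sits in the Cycle 1 column of Appendix A, which suggests few never-dosed subjects. This stands; the range of 1 to 5 has no basis in the documents.
- **The early-death figures are upper bounds.** A constant hazard fits poorly with the life-expectancy criterion. If that criterion predicted perfectly, there would be no deaths before week 6. This stands.
- **Early leavers should have a scan.** For the group described by "For those subjects that leave the study prior to completing Cycle 6, and who do not start another therapy", follow-up is timed from the End of Treatment scan, so the plan expects one. This narrows the strict-reading loss to deaths and missed scans. It does not help a subject who dies before any scan.
- **No imbalance is shown.** The documents give no evidence of unequal exclusion. True, but with open-label treatment both conditions can depend on the arm, and nothing in the rule guards against it.
- **A correctly named modified set with an all-randomized sensitivity analysis would also cure the label.** That is arguable for response. It is weak for OS, because death needs no scan.

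**Conclusion.** The concern holds: the sentence is wrong as written and should be corrected. Confidence is high that the label and the rule conflict. It is moderate that the rule governs OS, because that is inferred from the absence of any other population in the synopsis.

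The only exclusion certain under the rule is that of never-dosed subjects, whose number is unknown. On the strict reading, with a constant hazard and the protocol's own medians, the upper-bound distortion is +1.4 months in median OS, +3.6 points in 4-month PFS and +2.6 points in 6-month PFS (42.3% − 39.7%). Dropping a quarter of the early deaths gives +0.3 months, +0.9 points and +0.6 points. On the broad reading these early-death shifts are zero, but the analysis is still not intention-to-treat. The size and direction of any bias between arms cannot be obtained from the documents.

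**What to change.** Amend Statistical Methods, and any matching section of the full protocol or SAP, as follows:

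1. Make all randomized subjects, analysed as assigned, the primary set for OS, PFS and response.
2. Count death before the first scan as both a PFS and an OS event.
3. Keep subjects without a post-baseline assessment in the response denominator as non-responders.
4. State that every randomized subject, including the undosed, is followed for survival.
5. Report by arm the number without a post-baseline scan, and state how those still alive are handled for PFS.
6. Define *efficacy measurement*, and keep the dosed-and-measured set as a supportive analysis under its own name, not as intention-to-treat.

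The cost is a few sentences of wording, plus survival contact for probably a few undosed subjects, which the available text does not expressly plan. The reported estimates may become slightly less favourable.
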